### 3.4.3 Quantitative Assessment of Organizational Factors

During the main phase of the project, OAT site staff and administrators (average N=3 per site) will complete a survey at baseline and the end of follow-up phase. Provider-level Factors will include provider characteristics (e.g., socio-demographics, education and work experience) and their attitudes toward SHIM (or a theoretical integrated HCV care model at the SOC sites) and their

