For the secondary outcomes S2b-c, we will collect data using a **paper-based adherence form** administered by clinical personnel during patient visits at treatment initiation, medication pick-up at 4 and 8 weeks, and treatment completion at 12 weeks after initiation. The baseline form will assess self-efficacy and anticipated barriers to treatment adherence for the whole treatment period. The follow-up forms will assess treatment satisfaction, past 30-day and 7-day adherence using visual analog scale [36], side effects, reasons for non-adherence, and reasons for treatment discontinuation (if occurred). At treatment completion, the form will additionally assess the readiness and anticipated barriers to SVR check at 12 weeks after.

For the secondary outcomes S2a and S3a and relevant co-variables, we will collect data using a **patient survey**. The survey will be conducted for the pilot patients and all 3 arms of the main phase at baseline, treatment completion (or 12 weeks after initiation if not completed or 16 weeks after the baseline if not started) and 12 weeks after treatment completion (or 24 weeks after treatment initiation if not completed, or 28 weeks after the baseline if not initiated treatment).

The baseline survey will be administered after confirmation of the diagnosis using HCV RNA test. Patients who will test negative for HCV RNA will be excluded from the following study procedures.

All patient surveys will be collected by an independent interviewer, using study ID via UIPHP REDCap server with clerical checking and patient safeguards described in detail in the human subjects section.

The surveys will include demographics, geospatial assessment, depression (PHQ-9), substance use, alcohol use disorders (AUDIT-C), HIV comorbidity and treatment history, Chronic Liver Disease Questionnaire-Hepatitis C Version (CLDQ-HCV) [37], trust in physician scale [38, 39], HIV risk behaviors, family and social support [40], drug use and mental illness stigma [41], and socio-demographic information.

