### 3.5.8 Analytic plan

All analyses will be according to the principle of intent-to-treat, i.e., analysis of site and individuals within the site as randomized. The primary individual-level outcomes are achieving three elements of the HCV treatment cascade (diagnosed, treated, achieving SVR). We have powered the study based on a comparison of the proportions among the three groups (see below). The denominator for all cascade indicators is the number of OAT patients who are screened positive for HCV and are enrolled in the study. The numerators, the number who completed the pre-treatment evaluation, started DAA treatment and achieved SVR, will be obtained from the electronic clinical data collection system. Data will be assessed for missingness. A repeated measures likelihood based mixed model with missing at random (MAR) assumptions will be used for the analysis of the primary outcome to compare the three allocations, adjusted for the stratification variables (geographic region) plus age and gender. We will also adjust for covariates that are predictive of missingness to be consistent with the MAR assumption. Sensitivity analyses as described below will be done to assess this assumption, which is a reasonable starting point given missing data is expected to be low. Results will be displayed as point estimates with corresponding 95% confidence limits. The primary (and secondary) outcomes will be tested at the 5% (2-sided) significance level.

Hypotheses

1) OAT facilities implementing the simplified integrated model will have adoption and penetration of HCV care elements, that will ultimately result in improved patient-level outcomes like HCV cure compared to standard of care (SOC);

2) Compared to No ECHO, clinicians at ECHO-facilitated sites will have improved HCV care cascade outcomes.

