Aim 3's analysis will involve three distinct strategies. First, we will examine the time difference in HCV cascade elements (% diagnosed, % treated, % achieving SVR), with sub-analyses for geographic area and OAT dropout +/- ECHO vs SOC setting. To do this, we will use a generalized mixed linear model (with a logit link), where group will vary by either study arm or by geographical area. Our dependent variables will include: 1) a binary indicator for whether an individual patient achieved the desired HCV diagnosis/treatment coverage cut-off (e.g. diagnosis coverage >80%), as previously used to measure comprehensive and holistic integrated primary care for PWID receiving buprenorphine [42]. The same approach will then be used for secondary individual outcomes (treatment motivation and adherence, treatment satisfaction, quality of life), which we have done previously when integrating addiction treatment into specialty services in the US [43] and Ukraine [12]. 2) treating the primary and secondary indicators as a continuous variables. Any changes in national guidelines that might influence HCV treatment availability would not be scored until after at least 1 year after publication in order to allow for uptake changes by clinicians. Our covariates will include time trends, client-level variables including demographic characteristics, fibrosis stage, treatment motivation and adherence, addiction severity and mental health measures, as well as organizational and provider level measures (from Aim 2).

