In addition, we have planned to test for a linear trend among the intervention levels for the proposed outcomes, testing that SHIM+ECHO > SHIM with No ECHO > SOC. We also plan to test the treatment effects using similar methods for OAT dropout strata separately. In addition to direct effects, mediation and moderation regression will be conducted as described by Donaldson. Testing will be conducted at a Bonferroni corrected type I error level of 0.025 to control for multiple testing. Secondary and process outcomes will similarly be tested. These measures and their subscales will be compared as pre/post and over time using one-way ANOVA/Duncan test, with general linear models to identify differences in treatment effect stratified by the geographic region (cluster). Mean scores will be normalized, with comparisons between the three groups, with the referent being SOC. To address multiple testing, we will use the Benjamini-Hochberg method of controlling the false discovery rate. We do not expect missing data to be a concern since most of the data on primary outcomes will be derived from clinical source documentation; for the survey data, we expect that we will collect more than 90% of the data at the 24-week time point. We will, however, explore all patterns of missing data and compare those with and without data to determine whether the data may be MAR or not MAR (i.e. eliminate the missing completely at random assumption). We will conduct sensitivity analyses using an appropriate missing data method, such as multiple imputation.

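### One-way ANOVA/Duncan is assigned to measures repeated on the same people, and it competes with a mixed model named for some of the same outcomes

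*Combined protocol and SAP*

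**What the plan says.** Section 3.5.8 (Analytic plan) gives the method for secondary and process outcomes: "These measures and their subscales will be compared as pre/post and over time using one-way ANOVA/Duncan test". The rest of that sentence adds general linear models, described only as stratified by region. Mean scores are then normalized, "with comparisons between the three groups, with the referent being SOC". No person term or clinic term is named. The text does not say whether time or arm is the ANOVA factor. Nor does it say whether arms are compared on change scores, visit by visit, or on all surveys together.

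Just before this, the same section gives another method. For the cascade outcomes, "we will use a generalized mixed linear model (with a logit link"); then, "The same approach will then be used for secondary individual outcomes (treatment motivation and adherence, treatment satisfaction, quality of life"). A repeated-measures mixed model does appear in the section, but it "will be used for the analysis of the primary outcome to compare the three allocations".

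The measures are collected as follows:
- **Patients (3.5.6):** "The survey will be conducted for the pilot patients and all 3 arms of the main phase at baseline, treatment completion" (or a substitute date), and again 12 weeks after completion. Section 3.5.5 puts the SF-12 at four interviews, whereas 3.5.6 and its schedule show three.
- **Staff (3.4.3):** about three people per site "will complete a survey at baseline and the end of follow-up phase". Further organizational scales are completed twice a year.
- **Single-occasion endpoints (3.5.5):** motivation is scored at baseline only. Satisfaction and visual-analog adherence are defined at treatment completion, although the forms in 3.5.6 also collect them at earlier visits.

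**The concern.** A comparison of the same people before and after is the standard case in which one-way ANOVA's independence assumption fails. With time as the factor, stable differences between people stay in the error term. The test then becomes conservative and loses power, and Duncan's follow-up comparisons use the same error term. The general linear models in the same sentence are described only by their regional stratification, so they do not visibly repair this.

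This is a hybrid type 2 implementation study. Section 3.4.1 makes change over time in client, provider and organizational factors a subject of interest. Real change in quality of life, or in staff attitudes and self-efficacy, could be missed. An analyst would also have to choose between two methods for the same patient outcomes after seeing the data.

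**Working it through.** **Plan's own figure.** The documents give no power or error rate for these tests. The sample size in 3.5.9 (133 per group) concerns the primary comparison and does not bear on this point.

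**Inputs.**
- 160 patients per arm with a 10% loss of information (3.5.9) gives 160 × 0.9 = 144.
- Staff: 3 per site × 12 sites = 36, or 12 per arm (3.4.3).
- Two-sided level 0.05 (3.5.8).
- Within-person correlation ρ is not in the documents; 0.3, 0.5 and 0.7 are assumed.

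**Change test, two occasions.** Take n people with standard deviation σ at each occasion. One-way ANOVA assigns the mean change a variance of 2σ²/n. The true variance is 2σ²(1−ρ)/n. The ANOVA statistic is therefore the paired statistic multiplied by √(1−ρ), and it rejects only when the paired statistic exceeds 1.96/√(1−ρ). For a change that gives the paired test 80% power, the paired statistic centres on 1.960 + 0.842 = 2.802.

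| ρ | 1.96/√(1−ρ) | ANOVA power: Φ(2.802 − threshold) | True size: 2[1 − Φ(threshold)] |
|---|---|---|---|
| 0.3 | 2.343 | 0.677 | 0.019 |
| 0.5 | 2.772 | 0.512 | 0.006 |
| 0.7 | 3.578 | 0.219 | 0.0003 |

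Where the paired test has 90% power, ANOVA has 82%, 68% and 37%. With three occasions and 144 patients, simulated so that a repeated-measures test has about 80% power, ANOVA has 63%, 42% and 11%. At the 0.025 level that 3.5.8 also mentions, the two-occasion powers are 0.657, 0.465 and 0.156 against 80%.

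**Arm test, only if surveys are pooled as independent rows.** With m surveys per person the variance is inflated by D = 1 + (m−1)ρ. For three arms (2 degrees of freedom, critical value 5.991), the true size is exp[−5.991/(2D)].
- m = 3: D = 1.6, 2.0, 2.4. Size = 0.154, 0.224, 0.287. Simulation with 144 per arm gives 0.150, 0.216, 0.285.
- m = 2: D = 1.3, 1.5, 1.7. Size = 0.100, 0.136, 0.172, which is 2.0 to 3.4 times nominal.

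**Arm test on one value per person.** Simulated sizes for change scores or a single visit lie between 0.045 and 0.057. This is nominal, so there is no within-person inflation.

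**Clinic, a separate omission.** One-way ANOVA also ignores clinic. With 40 patients per clinic and an assumed intraclass correlation of 0.01 to 0.05 (not in the documents), D = 1 + 39 × ICC = 1.39 to 2.95. The same size formula gives 0.116 to 0.362 even with one value per person.

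**The case against.** The strongest reply is that 3.5.8 already assigns quality of life, adherence and satisfaction to a mixed model, with time trends among its covariates and indicators also treated as continuous. For those outcomes the defect is two unreconciled methods, not ANOVA alone. That stands. It does not clear the plan, because the mixed model is given a logit link and no stated person effect, and the ANOVA sentence follows it without saying which prevails.

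Second, Duncan's procedure is meant for several groups, and the next sentence compares three arms against SOC. Arm as the factor, on change scores or at each visit, is a fair reading and carries no within-person error. General linear models can also accommodate repeated measures. But the sentence speaks of pre/post and over-time comparison, names no person term, and on any reading leaves clinic out.

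Third, staff scales may not fall under this sentence. Section 3.4.4 gives Aim 2 its own plan, and 3.5.8 uses provider and organizational measures as covariates. The staff part is therefore conditional. However, the mixed model in 3.4.4 has dichotomous patient outcomes, so it does not test change in staff scores.

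Fourth, the two main hypotheses are between-arm, whereas the power loss concerns change over time. That limits the consequence to secondary and process findings.

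A reader might infer that arm comparisons will reject three to six times too often. The documents do not support that as a general statement. It requires three surveys pooled as independent rows at the 0.05 level with ρ of about 0.3 to 0.7, and the plan never says that surveys are pooled.

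**Conclusion.** The point holds for measures that are repeated on the same people: quality of life, the patient survey scales and, if the ANOVA sentence governs them, the staff and organizational scales. Used as written for change over time, one-way ANOVA is conservative for any positive within-person correlation. Power falls from 80% to roughly 68%, 51% or 22% at assumed correlations of 0.3, 0.5 and 0.7.

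The arm-test figures of about 15%, 22% and 29% apply only to three pooled surveys. It would also be wrong to infer that every secondary outcome is affected. Motivation is not, and neither are satisfaction and visual-analog adherence if they are analysed only at treatment completion, as 3.5.5 defines them. The primary outcome has its own repeated-measures model. Since 3.5.8 names two methods for some of the same outcomes, the plan needs a correction and a decision, not just more detail.

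**What to change.** Delete the one-way ANOVA/Duncan sentence and reconcile it with the mixed-model sentence in 3.5.8, so that each secondary and process outcome has one stated method. Say whether that method covers the staff and organizational scales.

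For continuous repeated scores, specify one linear mixed model with:
- all occasions, including baseline, as outcomes;
- fixed effects for arm, visit, arm-by-visit and region;
- a person random effect, or an unstructured within-person covariance;
- a clinic random effect with a small-sample correction for 12 clinics. A clinic intercept common to all visits cancels out of a difference in change, so let the clinic effect vary by visit where the data allow.

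From this model report the between-arm differences in change (SHIM vs SOC, SHIM+ECHO vs SHIM) and the within-arm changes. For the two-occasion staff survey, use the same model with both occasions as outcomes, or analyse the end score adjusted for baseline with a clinic term. Also settle whether the SF-12 is taken three or four times.

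The cost is SAP wording and standard software on data already planned. Reporting becomes slightly more complex, and between-arm intervals will widen once clinic is modelled.

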### 3.5.1 Design overview

Individual randomization of subjects within each site would likely lead to a high degree of cross-contamination between the study groups because the selected interventions are designed to sustainably change the provider knowledge and practice. Therefore, we have chosen a cluster-randomized trial design, where participating sites will be randomly assigned to one of the three implementation arms. Based on our preliminary studies suggesting region-specific differences in HCV level among OAT patients, we will stratify 12 OAT sites by 4 defined geographic regions (Center, East, South, West) at a 1:1:1:1 ratio. To achieve the desired sample size (see Sample Size section) and retain equal size in each group, we will select and match 3 clinics across the 4 regions. One clinic per triplet will be randomized to one of the three arms: Standard of Care, SHIM and SHIM+ECHO (see Study Conditions), resulting in total 4 clinics per arm. Each clinic will aim to recruit 40 patients. In case of clinic's capacity the availability of DAA medication in region, the clinic's capacity to include in treatment and monitor the course of treatment of a larger number of patients) the number of participants can be increased up to 60). All sites will follow the same patient recruitment and data collection procedures.

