### 3.5.2 Site eligibility and selection

To participate in the study, each OAT site will need to meet the following criteria: (a) at least 100 patients receiving OAT; and (b) regional administrator approval for the site to receive the DAA medications and its clinicians to participate. Before the start of the first year of the main phase of the project there were 202 OAT sites in Ukraine, with 34 having over 100 patients (12, 10, 7, 5 sites in Center, East, South, West, respectively) and 21 have over 150 patients. OAT sites are minimally staffed with 1 narcologist and two nurses; the number of counselors and case managers may vary. After we define the three sites from each region, we will randomize them into one of the three study arms.

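### Within-region tests of treatment effect, and the 94% power claimed for them, are not supported by a design with one clinic per arm in each region

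*Combined protocol and SAP*

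**What the plan says.** **Design.** Section 3.5.1 states: "we will select and match 3 clinics across the 4 regions", then "One clinic per triplet will be randomized to one of the three arms: Standard of Care, SHIM and SHIM+ECHO". Section 3.5.2 confirms it: "After we define the three sites from each region, we will randomize them into one of the three study arms". The result is four regional triplets, 12 clinics and four clinics per arm. On size: "Each clinic will aim to recruit 40 patients", with up to 60 allowed where capacity permits.

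**Analysis.** For the cascade outcomes, section 3.5.8 plans a logit-link mixed model "with sub-analyses for geographic area and OAT dropout +/- ECHO vs SOC setting". For secondary and process measures, compared before and after and over time, it plans "general linear models to identify differences in treatment effect stratified by the geographic region (cluster"; the last word of that phrase labels the region as the cluster.

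**Power.** Section 3.5.9 states 94% power at a Bonferroni-corrected 2.5% type I error rate to detect a standardized effect of 0.32 inside each geographic stratum. It also expects a 10% loss of information.

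No ICC, design effect or between-clinic variance appears anywhere. A site random effect is named only in the Aim 2 model (section 3.4.4). Nothing labels the regional analyses descriptive or notes that arm and clinic coincide within a region.

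**The concern.** A stated power and alpha imply a hypothesis test, so section 3.5.9 makes it hard to read the regional analyses as description only. Within a region, however, any difference between arms is a difference between single clinics. If SHIM looks better than standard of care in one region, the data there cannot say whether the model or the clinic is responsible. A p-value from the three-arm regional comparison can be obtained only by treating patients as the independent units, which leaves clinic variation out of the error term.

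At stake are statements that the effect is present in one region and absent in another. With ordinary variation between clinics, such statements would arise often when no regional difference exists.

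**Working it through.** **1. Reproducing the 94%.** Inputs: effect 0.32, read as Cohen's w (an assumption); 3 clinics x 40 = 120 patients per region; patients independent. The noncentrality is N x w² = 120 x 0.1024 = 12.29.

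- 1 df, two-sided 0.05 (0.025 per tail): Φ(0.32 x √120 - 1.96) = Φ(1.545) = 93.9%.
- 1 df, two-sided 0.025: Φ(3.505 - 2.241) = 89.7%.
- Three groups, 2 df, 0.025 (the plain reading): 83.0%. After the 10% loss (108 patients): 78.2%.
- Three groups, 2 df, 0.025, N = 160: 93.1%, but 160 is the size of an arm, not of a region.

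All of these set between-clinic variance to zero.

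**2. Counting degrees of freedom with the clinic as the unit.**

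- Within a region: 3 clinics - 3 arm means = 0 error df.
- Whole trial, region and arm as main effects: 12 - 4 - 2 = 6 error df.
- Whole trial with full arm-by-region interaction, which takes (3 - 1) x (4 - 1) = 6 df: 6 - 6 = 0 error df.

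A clinic random effect does not help, because a region has no second clinic in any arm from which to estimate it.

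**3. What a patient-level test would do if there were no effect anywhere.** Assumptions: m = 40 x 0.9 = 36 analysable patients per clinic, a binary outcome, and ICC from 0 to 0.10 (not in the documents). Design effect DE = 1 + (36 - 1) x ICC. Per-region rejection at 0.025: p = P(χ²₂ > 7.378/DE) = exp(-7.378/(2 x DE)). At least one of four regions: 1 - (1 - p)⁴. Arm-by-region test at 0.025: P(χ²₆ > 14.45/DE).

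| ICC | DE | Per region | Any of four | Arm-by-region |
|---|---|---|---|---|
| 0 | 1.00 | 2.5% | 10% | 2.5% |
| 0.01 | 1.35 | 6.5% | 24% | 10% |
| 0.05 | 2.75 | 26% | 70% | 51% |
| 0.10 | 4.50 | 44% | 90% | 78% |

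Beta-binomial simulation at 50% success gave 6.5%, 27.4% and 47.9% per region, and 23.5%, 72.2% and 92.8% for any region, at ICC 0.01, 0.05 and 0.10. With 40 patients per clinic the rates are slightly higher.

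**The case against.** **The quoted sentence concerns secondary and process measures.** True. For measures with a baseline, a before-after comparison removes stable clinic differences, though not clinic-by-time differences. The rates above are for a binary outcome without a baseline, so they describe the cascade outcomes and not that sentence. The cascade is reached through the geographic sub-analyses in section 3.5.8 and through section 3.5.9.

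**No arm-by-region term is named.** Also true: stratifying by region could mean adjusting for it. But the sentence seeks differences in treatment effect, and section 3.5.9 attaches power and alpha to each stratum. The within-region test therefore rests on the text, while the formal interaction test is an inference.

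**Regional effects are not wholly beyond estimation.** A reader might infer that no regional SHIM effect can be tested at all. That goes too far. Each region has two SHIM clinics and one standard-of-care clinic. Four region terms, four regional SHIM effects and one common ECHO effect make 9 parameters for 12 clinics, leaving 3 error df. Such a test would be much weaker and depends on the common-ECHO assumption, and the plan does not specify it.

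**The size depends on an unknown ICC.** This stands. At ICC 0 there is no excess, and the 10% for any region is multiplicity alone. Matching clinics within regions may lower the relevant variance. The table does not apply the Benjamini-Hochberg step in section 3.5.8; that step adjusts p-values but cannot correct ones built on the wrong error term.

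**Main comparison and scale-up.** A reader might infer that the overall arm comparison is compromised, or that regional findings will direct scale-up. The documents support neither. The primary model in section 3.5.8 adjusts for region without an interaction, the stated hypotheses are overall comparisons, and nothing says that regional results will decide where SHIM is rolled out.

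**Conclusion.** The point holds for three-arm tests within a region and for a full arm-by-region interaction. That part follows from the clinic counts alone: 0 error df in each case. The 94% in section 3.5.9 is not a property of this design; it is approached only with about 120 independent patients per region and a 1-df test at 0.025 per tail, and the three-group reading at 0.025 gives 83.0% even then.

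The practical size is conditional. Under the assumptions above, false-positive rates per region run from the nominal 2.5% at ICC 0 to 44% at ICC 0.10. The protocol itself studies provider and organizational influences on the cascade, so an ICC of exactly zero is not what it expects, but it gives no figure. The pooled comparison, with region as a main effect and four clinics per arm, is not affected by this point. The plan should be changed, but the fault lies in subsidiary analyses.

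**What to change.** - Section 3.5.9: delete the statement of 94% power within geographic strata.
- Section 3.5.8: drop hypothesis tests of treatment effect within region and of arm-by-region, for both the cascade and the secondary measures. Report region-by-arm results descriptively, labelled as single-clinic values.
- Section 3.5.8: name the clinic, not the region, as the cluster.
- Keep region as the stratification factor in the overall arm comparison, with between-clinic variation (6 df) as its error term.

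The cost is SAP wording. Sites, patients and data collection do not change. The sponsor gives up region-specific p-values, which the design cannot support.

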In the second part of the analysis, we will examine the role of barriers and facilitators measured using the multi-level framework that includes client-, provider-, organizational-, community-level variables. First, using principal component analysis (PCA), we will identify various dimensions of clinician and organizational behavior that might influence HCV care integration into OAT settings through adoption and implementation of SHIM +/- ECHO at each site, which would summarize the variability in the data. PCA, a transformation used for data reduction, will be applied to multi-level organizational variables. Each principal component represents a different weighted average of the various organizational and client level variables, and each explains a different aspect of the variation observed in patterns of the organization and staff member. Principal components are important ways to group variables that are independent of each other by design, which addresses the issue of multicollinearity [33, 34], which can undermine various modeling strategies. To test the extent to which the barriers and facilitators are associated with higher or even increasing HCV diagnosis, treatment initiation and SVR achievement, we would estimate, using a generalized linear mixed model in which the outcome would be measured at the patient level (level 1), as a dichotomous variable of having been diagnosed/treated/cured or not. Among the covariates in the model, we would include an additional parameter that would incorporate the random effects associated with each provider (level 2), and a random effect associated with each site (level 3), which would be modeled as a function of estimated barrier and facilitator principle components.

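### Clinics are randomised, but no Aim 3 model specifies a clinic effect, and region is labelled the cluster; if clinic is left out, the nominal 5% error is not held

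*Combined protocol and SAP*

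**What the plan says.** All references are to the combined protocol and SAP.

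- **Randomised unit (3.5.1).** The text says that "participating sites will be randomly assigned to one of the three implementation arms". Three clinics are matched in each of four regions, and "One clinic per triplet will be randomized to one of the three arms: Standard of Care, SHIM and SHIM+ECHO", "resulting in total 4 clinics per arm". Each clinic aims for 40 patients and may go up to 60.
- **Primary analysis (3.5.8, first paragraph).** "A repeated measures likelihood based mixed model with missing at random (MAR) assumptions will be used for the analysis of the primary outcome", adjusted for region, age and gender and for covariates that predict missingness. No random effect is listed. Tests are two-sided at 5%.
- **Cascade analysis (3.5.8, first of the three strategies).** A "generalized mixed linear model (with a logit link), where group will vary by either study arm or by geographical area". One dependent variable is "a binary indicator for whether an individual patient achieved the desired HCV diagnosis/treatment coverage cut-off (e.g. diagnosis coverage >80"%).
- **Secondary and process outcomes (3.5.8, last paragraph).** One-way ANOVA with Duncan's test, and "general linear models to identify differences in treatment effect stratified by the geographic region (cluster").
- **Aim 2 (3.4.4).** The barrier and facilitator model does contain "a random effect associated with each site (level 3") and a provider effect. That model does not compare arms.
- **Sample size (3.5.9).** 133 per group for 90% power at 5%, inflated only for a 10% loss of information. No ICC or design effect is given.

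**The concern.** In a cluster-randomised trial the arm comparison must be judged against variation between clinics. Region cannot stand in for clinic. It is a blocking factor that contains all three arms, so adjusting for it removes differences between regions and leaves differences between clinics within a region untouched. If those differences are ignored, confidence intervals are too narrow and p-values too small. A chance difference between four clinics and four others can then be reported as an effect of SHIM or ECHO. The Summary says that a positive result would be used to argue for scale-up in Ukraine and internationally.

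The coverage indicator adds a further difficulty. Coverage above 80% is normally a property of a clinic, yet the text assigns it to an individual patient and does not define it.

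**Working it through.** **1. The plan's own figure.** For a two-group comparison of individuals with standardised difference 0.40 (effect size 0.20 on the f or w scale), n per group = 2(1.96 + 1.2816)²/0.40² = 131.3, so 132. The t-test version gives 132.3, so 133. The stated 133 is therefore reproduced by a formula with independent patients and no design effect. As the three-group 2-df test that 3.5.9 describes, 399 patients would give 95.6% power, not 90%. That mismatch is a separate matter.

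Section 3.5.9 also claims 94% power within each region. Each region has one clinic per arm, so arm and clinic are completely confounded there and no between-clinic error is left. Such a test is possible only with patients as the unit.

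**2. Inputs for the error rate.** From 3.5.1 and 3.5.8: 12 clinics in 4 regions by 3 arms, 40 per clinic, two-sided 5%. Assumed, because the documents give none: a within-region ICC of 0.01 to 0.10.

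**3. If no clinic term is fitted.** The design effect is DE = 1 + 39 × ICC. The pairwise error is 2[1 − Φ(1.96/√DE)]. The three-arm error is P(DE × χ²₂ > 5.99) = 0.05^(1/DE). The simulation used clinic probabilities drawn from a beta distribution, a logistic model with region but no clinic term, 4,000 runs per setting, and base rates of 30%, 50% and 70%.

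| ICC | DE | Pairwise, formula | Pairwise, simulated | Three-arm, formula | Three-arm, simulated |
|---|---|---|---|---|---|
| 0 | 1.00 | 5.0% | about 5% | 5.0% | about 5% |
| 0.01 | 1.39 | 9.6% | 9–10% | 11.6% | 12% |
| 0.02 | 1.78 | 14.2% | 14–15% | 18.6% | 19–20% |
| 0.05 | 2.95 | 25.4% | 26–27% | 36.2% | 37–39% |
| 0.10 | 4.90 | 37.6% | 37–39% | 54.3% | 55–58% |

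The simulation adjusts for region and still agrees with the formula, so region adjustment does not cure the problem. With 60 per clinic, the three-arm error by formula is 15%, 25%, 47% and 65% at ICC 0.01, 0.02, 0.05 and 0.10. With 40 per clinic, the error reaches 15%, three times nominal, at an ICC of about 0.015 (three-arm) or 0.022 (pairwise).

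**4. If a clinic intercept is fitted but tested with z.** Between-clinic degrees of freedom are 12 − 1 − 2 (arm) − 3 (region) = 6, and P(|t₆| > 1.96) = 9.8%. Simulation (20,000 trials per ICC, base rate 50%, clinic variance not allowed below zero) gives a pairwise error of 6.0%, 7.3%, 9.3% and 9.9% at ICC 0.01, 0.02, 0.05 and 0.10. With t on 6 df it is about 5% throughout. The region-blocked clinic-level F test on 2 and 6 df gives 4.4% to 5.8% in the step 3 simulation.

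**5. Power once clinic is respected.** With 36 evaluable per clinic (40 × 0.9, 432 in total) and w = 0.20, the noncentrality is 432 × 0.04/DE = 17.28/DE, where DE = 1 + 35 × ICC. The F(2,6) test then has power of 82% at ICC 0, 69% at 0.01, 59% at 0.02, 40% at 0.05 and 26% at 0.10.

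**The case against.** The strongest reply is that this is under-specification. Section 3.5.8 names mixed models for the cascade outcomes without listing their random effects, and it promises an intent-to-treat analysis of sites, and of individuals within them, as randomised. The authors write a site effect for the same cascade outcomes in Aim 2. In the logit model, the grouping by arm or area can be read as the comparison being made, not as the random-effect structure. A clinic intercept could be fitted without contradicting the text.

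This stands in part. A reader might infer that every Aim 3 model treats patients as independent and that the error rate is therefore several times 5%. The documents do not support that for P1 to P3. The sentence that labels region the cluster, and the ANOVA/Duncan tests, govern secondary and process measures. The inflation also depends on an ICC that nobody has stated: it is about twofold at 0.01 and absent at 0. The text does not specify z tests either.

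A reader might also infer that the coverage indicator turns 12 clinic values into 480 patient records. That is one reading of an undefined variable, and a patient-level indicator is possible.

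What the reply does not remove is that the randomised unit appears in none of the Aim 3 models, while region, age, gender, arm and area are all named. The Aim 2 site effect does not test arms. Repeated-measures wording ordinarily points to correlation within a patient, not within a clinic.

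**Conclusion.** The point holds in two strengths. For secondary and process outcomes the written rule is wrong: region is not the cluster, and one-way ANOVA/Duncan treats patients as independent. For P1 to P3 the clinic effect is unspecified, so the stated 5% level is not secured. If clinic is omitted, the real error is about 10% to 39% pairwise and 12% to 56% for three arms over ICC 0.01 to 0.10. If clinic is included but tested with z, it is up to about 10%. These figures assume 40 per clinic and an ICC range chosen for illustration. They show what would follow from each choice and do not establish what the sponsor will do. The choice must be fixed before outcome data are compared by arm, because results under the competing models could differ materially.

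**What to change.** - For each of P1, P2 and P3, specify one binary record per enrolled patient, with fixed effects for arm, region, age and gender, a random clinic intercept, and t/F inference on about 6 between-clinic degrees of freedom.
- Cross-check with a clinic-level analysis blocked by region (arm plus region, F on 2 and 6 df).
- Use the same clinic term for secondary and process outcomes in place of ANOVA/Duncan, and stop calling region the cluster.
- Define the coverage indicator as a patient-level outcome, or analyse it at clinic level with 12 observations.
- In 3.5.9, state an assumed ICC range and restate power. Withdraw the within-region power claim, or label it descriptive.

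The wording and code changes are small, and no extra data are needed. The real cost is wider confidence intervals and power below the stated 90%. By the calculation above, the clinic-level three-arm test has about 69% power at ICC 0.01 and 40% at 0.05 for the effect size used in 3.5.9.
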